Pregnancy outcomes and medical costs according to gestational diabetes mellitus diagnostic criteria: randomized prospective study. POMECS study.

Protocol ID: 00003

Approval Number: 11/09/2016

Version: 8th January 2018

Due to Hyperglycemia and Adverse Pregnancy Outcomes study results, a new gestational diabetes mellitus (GDM) diagnostic criteria was defined using a one-step approach (75-g oral glucose tolerance test -OGTT-) ¹

However, not all scientific societies have accepted and have implanted this new diagnostic criteria. The lowest glycemia cut-off of this criteria regarding the two-step approach entails an increase in GDM incidence with discordant studies about its cost-effectivity ²⁻⁴.

It will be assessed if pregnancy outcomes and medical costs are different depending on diagnostic criteria used.

RESEARCH DESIGN AND METHODS

The POMECS study is a randomized, parallel group trial, conducted in Spain. The Ethics Committee at Hospital Universitari Mútua Terrassa (Spain) approved the study.

Participants:

All pregnant women with follow-up of their gestation at Hospital Universitari Mútua Terrassa (Spain), at first antenatal visit, will be proposed to participate in the study.

Inclusion Criteria:

- Age 18-50 years
- No expectation that the participant will be moving out of the area of the clinical centre during the next year
- Informed Consent Form signed by the subject

Exclusion Criteria:

- Pre-existing type 1 or 2 diabetes
- Advanced human immunodeficiency virus infection (on medications that cause hyperglycemia), severe liver disease, gastric bypass surgery or other illnesses/surgeries that preclude them from drinking the glucose solution.

Randomization:

All pregnant women without a former diagnosis of diabetes mellitus will be considered for gestational diabetes mellitus (GDM) screening at 24–28 weeks of gestation.

Women with risk factors for diabetes at their initial prenatal visit will be screening at 9-12 weeks of gestation. Risk factors are: Age >35years, obesity (body mass index $\geq 30\text{kg/m}^2$ or $>27.5\text{kg/m}^2$ in Asian Americans), first-degree relative with diabetes and high-risk race/ethnicity (e.g., African American, Latino, Native American, Asian American, Pacific Islander).

At the time of GDM screening, patients will be assigned a number by a random number generation program (ratio 1: 1) that will classify them to one of the following two groups:

- Experimental Group (One-step): International Association of Diabetes and Pregnancy Study Groups (IADPSG) Criteria.

Performing a fasting 2 hour 75g OGTT. The diagnosis of GDM is made if at least one or more values are \geq : Fasting 92, 1-hour 180, or 2-hour 153 mg/dL.

- Active Comparator (Two-step): National Diabetes Data Group (NDDG) Criteria

Step 1: Performing a 1h 50-g glucose load test (nonfasting). If the plasma glucose level measured 1 h after the load is \geq 140 mg/dL, proceed to a 100-g OGTT.

Step 2: 100-g OGTT. The diagnosis of GDM is made if at least two of the following four plasma glucose levels measured (fasting, 1 h, 2 h, 3 h after the OGTT) are \geq : 105mg/dl, 190mg/dl, 165mg/dl and 145mg/dl respectively.

If only one value is exceeded, 100g OGTT will be repeated 2-3weeks after.

Pregnant women without GDM diagnosis at third trimester of pregnancy will repeat GDM screening (according previous randomization) if it appears macrosomia or/and polyhydramnios in the follow-up.

GDM diagnosed women will be managed with diet and self-monitoring of blood glucose. Insulin will be added according to the local protocol⁵. All women will receive routine prenatal care (without differences between randomized groups).

Outcomes

Primary outcome Measures:

Large for gestational age (LGA): Infant birthweight >90th centile using customized growth curves. Time Frame: At birth of infant.

Secondary Outcome Measures:

1. Infant outcomes

- Small for gestational age (infant birthweight <10th centile using customized growth curves); macrosomia (infant birthweight \geq 4kg), Neonatal obstetric trauma (shoulder dystocia, clavicle fracture, brachial plexus injury, intrapartum asphyxia), Congenital anomalies (Coding of EUROCAT), Pregnancy loss (Miscarriage, stillbirth, neonatal death)

Time Frame: At birth of infant

- Neonatal hypoglycaemia (neonatal plasma glucose levels <2.5 mmol/L in the first 24 hours of life and <2.8 mmol/L thereafter), Neonatal hypocalcemia (neonatal calcium levels <7mg/dl), Neonatal hyperbilirubinemia (hyperbilirubinemia treated with phototherapy), Neonatal polycythemia (hematocrit from a peripheral venous sample >65 percent), Respiratory Distress Syndrome (onset of progressive respiratory failure shortly after birth, in conjunction with a characteristic chest radiograph -after ruling out other causes-), Hypertrophic cardiomyopathy (increased left ventricular -LV- wall

thickness ≥ 15 mm imaged anywhere in the LV wall -by transthoracic echocardiography-), NICU admission (NICU admission for treatment or surveillance), neonatal hospital stay (Length of hospital stay –days-).

Time Frame: at infant hospital discharge.

- Perinatal mortality (infant deaths that happen at less than 7 days of age and fetal deaths with a gestational age of 28 weeks or more). Time Frame: First 7 days postpartum.

2. Maternal outcomes

-Hypertension in pregnant: worsening of chronic hypertension, gestational hypertension and preeclampsia. Time Frame: First 3 months postpartum

- Polyhydramnios (Amniotic fluid index ≥ 25 cm). Time Frame: At birth of infant.

- Cesarean section delivery of a baby through a surgical incision in the mother's abdomen and uterus. Time Frame: At birth of infant.

- Maternal hospital stay: Length of hospital stay (days). Time Frame: at maternal hospital discharge.

- Questionnaires: Evaluation of Mediterranean diet adherence using Mediterranean Diet Adherence Screener (MEDAS) questionnaire. Evaluation of health-related physical activity using IPAQ questionnaire. Time Frame: up to 12-14weeks from last menstrual period.

3. Gestational age at delivery: Gestational age was defined as completed weeks based on last menstrual period or the earliest ultrasound assessment if discordant. Time Frame: At birth of infant.

4. Medical cost: economic cost include laboratory costs; glucose bottles (50 g, 100 g and 75 g); pharmaceutical expenditure (exact insulin doses consumed, total pens, needles, strips); medical visits during pregnancy and postpartum (endocrinologist, educational nurses, obstetrician and midwives); total number of tests (ultrasounds, cardiotocography records); cost of intensive care unit admissions (Length of stay and complexity) and total hospital admission costs. Time Frame: First 3 months postpartum

Statistical analysis

Sample size (n=3,644) was calculated to detect a 20% decrease rate of LGA (primary outcome), assuming baseline rate of 16.5% ($\alpha=0.05$ and $\beta=0.80$). This decrease rate was obtained from *St Carlos Gestational Diabetes Study*, carried out in Spanish population which compared Carpeten-Coustan criteria vs IADPSG criteria³. Since we will use NDDG criteria (vs. IADPSG), baseline LGA incidence was obtained from Spanish Multicentre Study⁶.

Results will be presented as means \pm standard deviation in normal distribution, median [interquartile interval (IQI)] in non-normal distribution or percentages. Normal distribution will be tested for each variable using the Kolmogorov test.

Student t test will be used for normally distributed variables and the Mann-Whitney U test for non-normally distributed variables between two independent groups.

Proportions will be compared using a Pearson's chi-square or Fisher exact test as appropriate.

We will use logistic regression analyses or multivariate linear regression (as appropriate) to estimate the ratio of the probability [I-TDS(1)] of occurrence of an adverse event (primary and secondary outcomes) with 95% CIs by experimental group versus control group adjusting for confounding factors (age, smoke habit, weight, multiparity) P values <0.05 were considered statistically significant. All statistical calculations will be performed with the STATA 14.0 statistical package.

REFERENCES

1. Metzger, B. E. *et al.* Hyperglycemia and adverse pregnancy outcomes. *N. Engl. J. Med.* **358**, 1991–2002 (2008).
2. Meltzer, S. J., Snyder, J., Penrod, J. R., Nudi, M. & Morin, L. Gestational diabetes mellitus screening and diagnosis: A prospective randomised controlled trial comparing costs of one-step and two-step methods. *BJOG An Int. J. Obstet. Gynaecol.* (2010). doi:10.1111/j.1471-0528.2009.02475.x
3. Duran, A. *et al.* Introduction of IADPSG criteria for the screening and diagnosis of gestational diabetes mellitus results in improved pregnancy outcomes at a lower cost in a large cohort of pregnant women: the St. Carlos Gestational Diabetes Study. *Diabetes Care* **37**, 2442–50 (2014).
4. Corcoy, R., Lumberras, B., Bartha, J. L., Ricart, W. & Grupo Español de Diabetes y Embarazo. New diagnostic criteria for gestational diabetes mellitus after the HAPO study. Are they valid in our environment?. *Endocrinol. Nutr.* **57**,

277–80

5. Asistencia a la gestante con diabetes. Guía de práctica clínica actualizada en 2014. *Av. en Diabetol.* **31**, 45–59 (2015).
6. Ricart, W. *et al.* Potential impact of American Diabetes Association (2000) criteria for diagnosis of gestational diabetes mellitus in Spain. *Diabetologia* **48**, 1135–41 (2005).

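### Randomisation window (9-12 versus 24-28 weeks) is fixed before assignment but missing from the planned models, and miscarriage and congenital anomalies need handling that respects it

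*Combined protocol and SAP*

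**What the plan says.** Under Randomization, all women without known diabetes are to be considered for screening at 24-28 weeks, but "Women with risk factors for diabetes at their initial prenatal visit will be screening at 9-12 weeks of gestation". The risk factors are age over 35, obesity, a first-degree relative with diabetes, and high-risk race or ethnicity. Allocation follows the screening schedule: "At the time of GDM screening, patients will be assigned a number by a random number generation program (ratio 1: 1". No stratification factor is named. Repeat screening in the third trimester keeps the earlier allocation, so the natural reading is that each woman is randomised once, at her first screen.

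Under Statistical analysis, the arms are compared with t, Mann-Whitney, chi-square or Fisher tests. They are also compared by logistic or linear regression for primary and secondary outcomes, "adjusting for confounding factors (age, smoke habit, weight, multiparity". There is no term for screening window and no estimate by window.

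The infant secondary outcomes, listed for all women, include "Congenital anomalies (Coding of EUROCAT), Pregnancy loss (Miscarriage, stillbirth, neonatal death".

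**The concern.** The window is known before assignment and costs nothing to record. It summarises four risk factors. Family history and ethnicity are not covariates at all, and age and weight carry the rest only in part. The window also sets how long a diagnosis can act before birth. Leaving it out gives up a little power, and the single pooled LGA estimate does not show how the effect looks in each group.

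The second issue is which outcomes the assigned criterion can affect. A criterion assigned at 24-28 weeks cannot cause anomalies that have already formed, and miscarriage can in practice follow only an early randomisation. The analysis plan nevertheless applies between-arm estimates and p-values to every secondary outcome across all women.

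**Working it through.** **Reproducing the plan's figure.** The Statistical analysis section says "Sample size (n=3,644) was calculated to detect a 20% decrease rate of LGA (primary outcome", "assuming baseline rate of 16.5"%, with alpha 0.05. The 0.80 printed as beta is read as power. A 20% relative decrease takes 16.5% to 13.2%, with mean 14.85%. For a two-sided test without continuity correction:

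n per arm = [1.96 √(2 × 0.1485 × 0.8515) + 0.8416 √(0.165 × 0.835 + 0.132 × 0.868)]² / 0.033² = 1,821.5, rounded up to 1,822. Doubled, this is 3,644, an exact match. Power at 1,822 per arm is 80.01%.

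**Time after randomisation.** Taking 40 weeks as term (an assumption), early women have 40 − 12 = 28 to 40 − 9 = 31 weeks left. Routine women have 40 − 28 = 12 to 40 − 24 = 16 weeks.

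**Gain from using the window.** The documents give neither the share screened early (f) nor the ratio of LGA rates, early to routine (R). I assume f = 0.3-0.6 and R = 1.5-2.5, with the overall rate held at p = 0.165:

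- Routine rate pr = p / (fR + 1 − f); early rate pe = R × pr.
- Share of outcome variance removed: g = 1 − [f pe(1 − pe) + (1 − f) pr(1 − pr)] / [p(1 − p)], where p(1 − p) = 0.1378.
- Effective n per arm = 1,822 / (1 − g); equivalent saving = 3,644 × g women.

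| | f | R | pe | pr | g | Women | Power |
|---|---|---|---|---|---|---|---|
| Smallest gain | 0.6 | 1.5 | 0.190 | 0.127 | 0.7% | 26 | 80.3% |
| Largest gain | 0.3 | 2.5 | 0.284 | 0.114 | 4.4% | 162 | just over 81.7% |

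The gain is about 0.3 to 1.7 points. A separate calculation, using a size-weighted stratified risk difference with a 20% reduction in both windows, gives 80.25% and 81.56% for the same two cases. Both calculations compare with an unadjusted test. The planned model already contains age and weight, so the further gain is smaller; the documents do not allow it to be estimated.

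**What the gain means in the planned model.** These variance formulas apply to a marginal risk difference. In a logistic model the extra covariate raises power but does not narrow the interval for the conditional odds ratio.

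**Why a by-window table is still useful.** If the 20% reduction occurred in one window only, the pooled effect would be diluted. With f = 0.4 and R = 1.5 (pe = 0.206, pr = 0.1375), an effect confined to routine women gives an overall rate of 0.4 × 0.206 + 0.6 × 0.1375 × 0.8 = 0.1485 and power of 27.7%. An effect confined to early women happens to give the same figures. Over f = 0.2-0.6 and R = 1-2, power is 10-60% (routine only) or 8-55% (early only). A covariate would not recover that power. The table would only make a diluted result easier to read.

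**Outcomes against randomisation time.**

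| Outcome | Randomised at 9-12 weeks | Randomised at 24-28 weeks |
|---|---|---|
| LGA | can be affected | can be affected |
| Stillbirth, neonatal death | can arise after assignment | can arise after assignment |
| Miscarriage | can arise after assignment | in practice cannot (no gestational cut-off is given) |
| Congenital anomalies | recorded at birth | formed before assignment |

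**The case against.** The strongest reply is that pooling is legitimate. Allocation is 1:1 whatever the window, and the stated question is whether outcomes and costs differ by diagnostic criterion across all screened women. LGA can arise in both groups. This stands: a reader might infer that the pooled comparison is biased or its p-value invalid, and the documents do not support that. Chance imbalance in the at-risk share between arms is also small, with a 95% range of about ±2.6 to ±3.2 percentage points for at-risk shares of 0.2 to 0.5.

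The precision argument is also modest. Age and weight partly carry the grouping, so the plan does not disregard it altogether, and calling the gain free precision would be wrong for a conditional odds ratio. This stands too and is reflected in the figures.

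It is tempting to think that estimates by window would show whether early or routine use of the criteria drives an effect. They cannot. Window is set by risk status and not by randomisation, so timing is confounded with age, obesity, family history and ethnicity. The text also leaves open whether at-risk women who test negative early are screened again at 24-28 weeks, so the early group may contain both uses.

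On outcomes, miscarriage is one component of pregnancy loss, and the other two components can arise in both groups. The composite as a whole is therefore not confined to one window. Restricting miscarriage to early women changes its denominator and, in practice, not its count. Recorded anomalies could also differ between arms through detection, for example if the number of ultrasounds differs. That would be a difference in ascertainment and not an effect of the criterion on anomalies already formed, which is a further reason for descriptive reporting.

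**Conclusion.** The point holds as a minor improvement. The plan leaves a pre-randomisation grouping out of its models. Using it is worth about 0.3 to 1.7 points of power against an unadjusted test, on assumed values of f and R, and less beyond age and weight. The primary comparison is valid without it.

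Estimates by window are worth having as description and cannot isolate timing. The outcome point is narrow: it concerns the miscarriage component's denominator and a between-arm test of anomalies that, for women randomised at 24-28 weeks, formed before assignment. It assumes that miscarriage is defined so as to exclude losses after 24 weeks, which the protocol does not state.

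**What to change.** - Record randomisation window (9-12 versus 24-28 weeks) and add it as a covariate in the LGA and secondary-outcome models. If a gain in precision is wanted as well as power, report a marginal risk difference or risk ratio from the adjusted model.
- Pre-specify the arm effect on LGA by window, labelled supportive and imprecise, with a statement that window is confounded with risk status and cannot separate early from routine use of the criteria.
- Clarify in the protocol whether at-risk women who test negative early are screened again at 24-28 weeks.
- Define miscarriage and tabulate it with women randomised at 9-12 weeks as its denominator. Keep stillbirth and neonatal death for all women.
- Report congenital anomalies descriptively by arm, without a between-arm test.

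The cost is one covariate, one table and a few sentences of text. Randomisation does not change.

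### Three neonatal outcomes rest on a blood value alone, and the plan neither equalises newborn testing between arms nor records who was tested, so label-driven testing could bias them undetected

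*Combined protocol and SAP*

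**What the plan says.** Under Secondary Outcome Measures, Infant outcomes, three conditions are defined by a laboratory threshold and nothing else: "Neonatal hypoglycaemia (neonatal plasma glucose levels <2.5 mmol/L in the first 24 hours of life and <2.8 mmol/L thereafter", "Neonatal hypocalcemia (neonatal calcium levels <7mg/dl" and "Neonatal polycythemia (hematocrit from a peripheral venous sample >65 percent". Their time frame runs to the infant's hospital discharge. The same list ties a fourth condition to treatment given: "Neonatal hyperbilirubinemia (hyperbilirubinemia treated with phototherapy".

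The introduction says of the one-step criteria: "The lowest glycemia cut-off of this criteria regarding the two-step approach entails an increase in GDM incidence". The diagnostic rules point the same way. In the one-step arm, "The diagnosis of GDM is made if at least one or more values are" at or above the cut-offs. The two-step arm needs a positive 50-g test and then at least two of four raised values on the 100-g test.

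The only statement on equality of care is "All women will receive routine prenatal care (without differences between randomized groups". It does not reach the newborn. The Statistical analysis section compares secondary outcomes by arm, adjusting for age, smoking, weight and multiparity. The documents do not say which newborns have blood drawn, when, or for what reason. They do not say how an untested infant is classified, or whether neonatal staff know the mother's diagnosis.

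**The concern.** An infant who is never sampled cannot meet a blood-value definition. The recorded frequency therefore depends on who is tested as well as on who is ill. Here the treatment under study is a labelling rule, so the GDM label is a consequence of allocation. If the label also influences whether a newborn is tested, the proportion tested will differ between arms. Randomization does not protect against that, and the planned covariates do not address it because the imbalance arises after randomization.

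The trial is meant to inform a choice between two sets of criteria. An apparent excess of neonatal hypoglycaemia in the one-step arm could be an effect of testing, and a true reduction could be cancelled. As planned, a reader of the results could not tell these apart, because testing is not recorded as data.

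**Working it through.** **The plan's own figure.** The only size calculation is for LGA: 16.5% against 16.5% × 0.80 = 13.2%, alpha 0.05 two-sided, power 0.80 (printed as β). The standard two-proportion formula with pooled variance and no continuity correction gives 1,822 per arm, 3,644 in total, which matches the plan. I use 1,822 per arm below.

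**Model.** For each arm,

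recorded rate = r × [g × sL + (1 − g) × sU]

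where r is the true rate (equal in both arms), g is the share of mothers labelled GDM, and sL and sU are the testing proportions for infants of labelled and unlabelled mothers. Untested infants are counted as non-events. The ratio between arms does not depend on r.

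**Inputs.** The documents give only the direction of the difference in g. All values of g, sL, sU and r here are assumptions: g = 20% (one-step) vs 10% (two-step), sL = 100%.

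**No true difference, r = 10%.**

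- sU = 15%: 0.10 × (0.20 + 0.80 × 0.15) = 3.20% vs 0.10 × (0.10 + 0.90 × 0.15) = 2.35%; ratio 1.36.
- sU = 50%: 0.10 × (0.20 + 0.80 × 0.50) = 6.00% vs 0.10 × (0.10 + 0.90 × 0.50) = 5.50%; ratio 1.09.
- sU = 100%: 10.0% vs 10.0%; ratio 1.00.

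**Chance of a false finding** (two-sided P<0.05, normal approximation, 1,822 per arm). For sU = 15% and r = 10%, the difference is 0.0085 and its standard error is √(2 × 0.02775 × 0.97225 / 1,822) = 0.00544, a standardised difference of 1.56. The chance of significance is about 34%.

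| sU | true rate | chance of P<0.05 |
|---|---|---|
| 15% | 10% | about 34% |
| 15% | 5% | about 20% |
| 15% | 2% | about 11% |
| 50% | 10% | about 10% |
| 100% | any | 5% (nominal) |

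**Wider range at r = 10%.** With labels 15% vs 10% and sU = 20%, the rates are 3.20% vs 2.80%: ratio 1.14, chance about 11%. With labels 30% vs 10% and sU = 5%, they are 3.35% vs 1.45%: ratio 2.31, chance about 96%.

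**Masking.** If the one-step arm truly lowered the rate by 20%, the recorded ratio with labels 20% vs 10% would be 0.80 × 1.36 = 1.09 at sU = 15%, 0.80 × 1.09 = 0.87 at sU = 50%, and 0.80 at sU = 100%.

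**Analysing tested infants only.** With sU = 15%, the tested share is 0.20 + 0.80 × 0.15 = 32.0% in the one-step arm and 0.10 + 0.90 × 0.15 = 23.5% in the two-step arm. Infants of labelled mothers make up 0.20/0.320 = 62.5% of those tested in one arm and 0.10/0.235 = 42.6% in the other. The tested groups are no longer comparable, so this restriction does not repair the comparison.

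**The case against.** The strongest objection is that the causal link is missing from the documents. A reader might infer that newborns are sampled mainly because of the maternal label, that untested infants will be scored as non-events, and hence that the one-step arm will record more events. None of this is written. The plan is silent on newborn sampling, and silence is not selective sampling. The local guideline is cited for insulin, and its content on newborns is not available here. Untested infants could equally be treated as missing. This stands: the point must be conditional.

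The size is also open. If tests in unlabelled infants are prompted by clinical signs, more of the true cases are found than the testing share suggests. If half are found, the ratio is 1.09 whatever share was tested. The 34% figure needs a true rate of 10%, and nothing in the documents supports that rate for any of the three conditions. This stands too, which is why the small-bias and no-bias cases are shown.

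A third objection is that a treatment-based definition does not remove the problem: an infant tested because of the label, found low and treated still counts, while an untested infant without signs does not. That is correct, and it argues against replacing the prespecified definitions. It does not argue against recording testing. Nothing in the plan would reveal whether testing differed, and that gap remains after every objection.

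**Conclusion.** The point holds in conditional form. The documents establish threshold-only definitions, an expected difference in GDM labelling between arms, no common rule for newborn testing, no described blinding of neonatal staff, and no handling of untested infants. If testing follows the label, the threshold-based comparison is biased against the one-step arm. If testing does not depend on the label, this bias is zero.

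Under the main assumptions the recorded ratio runs from 1.36 down to 1.00 as testing of other infants rises from 15% to 100%. The documents do not support the stronger conclusion that the comparison is certainly biased, and they fix no particular size. Only secondary outcomes are concerned. LGA is based on birthweight, so neither it nor the sample size of 3,644 is exposed to this mechanism. It is a worthwhile and inexpensive improvement that does not threaten the primary result.

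**What to change.** Keep the three threshold definitions and make these changes in the outcome definitions and the Statistical analysis section:

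- Record for every newborn whether glucose, calcium and hematocrit were each measured, and why (routine because of maternal GDM, or a clinical sign).
- Report the proportion tested by arm for each test.
- State how untested infants are handled, and do not silently count them as non-events.
- Add a between-arm outcome for each condition: a low glucose, low calcium or high hematocrit value that was symptomatic or had treatment recorded. This follows the approach already taken for hyperbilirubinemia.
- If testing differs by arm, state that the threshold-based comparison is not unbiased and that restricting it to tested infants does not repair it.

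The cost is some wording and two chart-abstraction fields per test. No extra blood sampling and no change in sample size are needed. The added outcomes will have fewer events, and some label effect will remain in them, because a tested infant is also more likely to be treated.

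### The newborn hypertrophic cardiomyopathy outcome uses a fixed 15 mm wall thickness with no scaling to newborn size, so a near-zero count would not inform about size-relative hypertrophy

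*Combined protocol and SAP*

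**What the plan says.** In the combined protocol and SAP, Outcomes, Secondary Outcome Measures, item 1 (Infant outcomes) lists "Hypertrophic cardiomyopathy (increased left ventricular -LV- wall" thickness, with the threshold given as at least "15 mm imaged anywhere in the LV wall" on transthoracic echocardiography. The group it belongs to carries "Time Frame: at infant hospital discharge", so the heart being measured is a newborn's. No weight, body surface area, gestational age or neonatal reference enters the rule, and no source is cited for the 15 mm.

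The same section scales to size elsewhere. The primary outcome is "Infant birthweight >90th centile using customized growth curves", and small for gestational age uses the same curves. The neighbouring glucose, calcium and hematocrit outcomes carry thresholds set out for neonates.

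The Statistical analysis section plans chi-square or Fisher tests for proportions, and adjusted regression with 95% CIs for primary and secondary outcomes, at P < 0.05. It gives no expected rate for this outcome. The document does not say which newborns have an echocardiogram.

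**The concern.** This is a complete, stated rule rather than a detail left open. If 15 mm lies far above the range of newborn walls, the rule will classify infants with clearly thickened walls as unaffected. The planned comparison would then tend towards 0 versus 0. With no events an odds ratio cannot be estimated, and a reader could take the empty table as evidence that the two diagnostic criteria do not differ on this outcome. The trial exists to compare pregnancy outcomes between the criteria, so false reassurance on a neonatal outcome matters, although it is confined to one secondary item.

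**Working it through.** **1. The plan's own figure.** The only sample-size statement is for the primary outcome: "Sample size (n=3,644) was calculated to detect a 20% decrease rate of LGA (primary outcome), assuming baseline rate of 16.5"%. With p1 = 0.165, p2 = 0.8 × 0.165 = 0.132, two-sided alpha 0.05, power 80% (the document prints 0.80 as beta) and 1:1 allocation:

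n per arm = [1.960 × √(2 × 0.1485 × 0.8515) + 0.842 × √(0.165 × 0.835 + 0.132 × 0.868)]² / 0.033² = 1,822, total 3,644.

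This matches exactly. Trial size is not in dispute, and 1,822 per arm is used below.

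**2. Where 15 mm lies.** The documents give no newborn wall thickness, so these inputs are assumptions. Formulas: ratio = 15 / mean; z = (15 − mean) / SD.

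| Assumed mean, SD (mm) | Ratio | z |
|---|---|---|
| 3, 0.5 | 5.0 | 24 |
| 3, 1.0 | 5.0 | 12 |
| 5, 0.5 | 3.0 | 20 |
| 5, 1.0 | 3.0 | 10 |
| 7, 1.5 (deliberately generous) | 2.1 | 5.3 |

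With a mean of 3-5 mm, a wall at twice normal is 6-10 mm and falls below the cut-off. For 15 mm to sit at z = 2, the mean newborn wall would have to be 13 mm with SD 1 mm, or 11 mm with SD 2 mm.

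**3. A second route, also an assumption.** If wall thickness scales with the cube root of body mass, 15 mm in an adult of 60-80 kg corresponds in a newborn of 2.5-4.5 kg to between 15 × (2.5/80)^(1/3) = 4.7 mm and 15 × (4.5/60)^(1/3) = 6.3 mm. Conversely, 15 mm in a newborn corresponds to about 36-48 mm in an adult.

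**4. What a rare outcome yields with 1,822 per arm.** The control rate is assumed. The chance of no event in either arm, at equal rates, is (1 − rate)^3,644. Power is from exact enumeration of Fisher's test.

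| Control rate | Expected control events | No event in either arm | Power for a halving |
|---|---|---|---|
| 0.001% | 0.02 | 96% | about 0 |
| 0.01% | 0.18 | 69% | about 0 |
| 0.05% | 0.9 | 16% | 0.02% |
| 0.1% | 1.8 | 3% | 0.5% |
| 0.5% | 9.1 | about 0 | 16% |
| 1% | 18.2 | about 0 | 34% |

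With no events in one arm, the other needs at least 6 for P < 0.05 (0 versus 5: P = 0.062; 0 versus 6: P = 0.031).

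**5. What zero events would show.** If every infant in an arm were scanned, 0 of 1,822 gives a one-sided 95% upper bound of 1 − 0.05^(1/1,822) = 0.16% for walls of 15 mm or more. It gives no bound on lesser, size-relative thickening.

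**6. What scaling would and would not achieve.** By the normal approximation, 80% power needs a control rate of about 2.5% for a halving, or 16.5% for a 20% reduction. At an assumed 1%, power for a halving is 42% (34% by Fisher). A cut-off of z above 2 would flag about 2.3% of healthy infants under normality: 0.0228 × 3,644 = 83 if all were scanned.

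**The case against.** The decisive step lies outside the documents, which give neither newborn wall thicknesses nor an event rate. The assumed mean and SD describe normal infants. They show that normal infants will not reach 15 mm, but they do not give the distribution among affected infants. This stands: an expected count of about zero is an extrapolation. However, two separate assumptions and a generous alternative point the same way, and nothing in the documents shows that 15 mm is workable in a newborn.

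A reader might infer that a null result would say nothing at all. That is too strong, because with complete scanning it would bound the rate of walls of 15 mm or more at about 0.16% per arm. Nor do the power figures isolate the cut-off: power is low here for any rare outcome.

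A reader might also infer that the scans could simply be reclassified with no added work. The documents do not support this. They do not say who is scanned, whether numeric wall thickness is recorded, or whether infant length is recorded.

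Finally, the plan claims no power for this outcome and plans no equivalence conclusion. Misreading a null as no difference is therefore a risk in reporting, not something the plan commits to. The outcome is one of many secondary outcomes and feeds no composite or testing hierarchy.

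**Conclusion.** The point holds for this one secondary outcome. The definition is absolute, unsourced and unscaled. On the assumptions shown, the cut-off lies 10-24 SD above the newborn mean (5.3 SD on the generous alternative). With a mean of 3-5 mm, it would count infants with walls at twice normal as unaffected. A result near 0 versus 0 would not be informative about size-relative hypertrophy. How rarely the outcome would be recorded cannot be fixed from the documents. A reader might extend the point to the trial's main comparison, but the documents do not support that: the primary outcome and its sample size do not depend on this item. The outcome should be redefined, and the correction to the text is small.

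**What to change.** - Replace the 15 mm cut-off with a definition scaled to newborn size (z-score or centile) against a named neonatal reference. The sponsor should choose and justify the cut-off, given that z above 2 flags about 2.3% of healthy infants.
- State which newborns are scanned. Apply the definition to infants who have an echocardiogram in routine care with wall thickness and body size recorded, and use scanned infants as the denominator, giving the number scanned in each arm.
- Report the outcome descriptively. Power may remain low, and a scanned subset need not be comparable between arms.
- If no scaled definition can be applied, remove the outcome from the tested secondary outcomes and do not interpret a null as no difference.

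The definition itself is a one-line change. The cost is that infants without a recorded thickness or body size cannot be classified, and whether those measurements exist has to be confirmed. A new threshold does not by itself resolve selective scanning.
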